### **6.5.1.2 Single Use Auto-Injector malfunction**

An AI device malfunction is when the AI device appears normal during verification of shipment and then does not work during administration, e.g., the autoinjector activated prematurely, the autoinjector stalled or did not expel the full volume, needle guard safety feature did not deploy or remain locked, glass syringe breakage, needle bent or broke upon use. Device malfunctions should be reported using the Device Malfunction Return Instruction and the Study Monitor should be notified.

Site staff will be asked to send back malfunctioning devices to the depot or local sponsor company according to local procedures. Address and attention for malfunctioning device is available in the Device Malfunction Return Instruction.

## **6.6 Investigational product administration and treatment compliance**

The administration of all study drugs (including IPs) should be recorded in the appropriate sections of the Case Report Form (CRF).

The IP will be administered at the study center for first 3 doses and at home for following 2 doses. IP administration should be done within visit windows as specified in

. All information regarding IP administration will be provided in the Instruction for Use (IFU).

### **Before investigational product administration**

Prior to each IP administration at study center:

- Investigator/authorized delegate will assess injection site as per standards of medical care
- For WOCBP, urine pregnancy test will be done; IP will be administered only when the result of the test is negative (see Section 5.2.4.1)

Prior to each IP administration in at-home setting:

- Investigator/authorized delegate will perform visit reminder call within 48h prior scheduled IP administration. The conversation should include only basic information and serve as a reminder to the patient about the next scheduled visit to occur within 48 hours after home administration.
- For WOCBP, urine pregnancy test will be done; IP will be administered only when the result of the test is negative (see Section 5.2.4.1)

### **Investigational product administration**

[figure not shown]
The IP will be administered by the Investigator/authorized delegate/patient/caregiver as specified in Table 2. If patient is not willing or not able to self-administer (or caregiver is not willing/able to administer) at Visit 4 patient will be discontinued from the IP.

It is suggested that the site of injection of the IP be rotated such that the patient receives IP at a different anatomical site each time. Suggested injection site rotation sequence is presented below (see Figure 3). In the case when rotation of the injection site is not favorable for the patient and/or Investigator, the reason should be recorded in the source documents. The injection site must be recorded in the source documents and the eCRF at each treatment visit.

If IP is self-administered by the patient, the injection should be done in the abdomen or thigh; when the injection is performed by the healthcare provider (HCP) or caregiver: in the abdomen, or thigh or upper arm (site reserved only for injections performed by HCP or caregiver - see Figure 3). The same person must administer the IP throughout the study, whether it is the patient or caregiver.

Further details on IP administration are provided in the Instruction for Use (IFU). Investigational product administration must be carried out in line with the instructions provided.

**Figure 3** Injection sites and rotation scheme

### **After investigational product administration**

After IP administration the patient should be observed for a minimum of 2 hours by the HCP (or responsible adult if injection was done at home) for the appearance of any acute drug reactions. Patient/caregiver will be trained by the study site on the use of epinephrine containing device that will be provided. If IP administration was performed at home, the patient should visit the study centre for the previously scheduled center visit within 48 hours after IP administration.

### **Conditions requiring investigational product administration rescheduling**

If any of the following occur, the Investigator should reschedule the visit and the IP should not be administered until the rescheduled visit:

- The patient has an intercurrent illness that, in the opinion of the Investigator, may compromise the safety of the patient in the study (eg, viral illnesses)

The patient and caregiver, if applicable, should be informed about these conditions and reminded prior to at-home administration. In case of any doubts before at-home administration, patient should contact study center.

## **6.7 Management of investigational product-related reactions**

Prior to the first 3 administrations, which will be performed in the clinic, patients will have had a pre-assessment (ie, vital signs) prior to IP administration, and will be observed after IP administration for a minimum of 2 hours for the appearance of any acute drug reactions.

Study personnel should inform patients that, for subsequent administrations, they should be observed for 2 hours after IP administration for the appearance of any acute drug reactions. As with any medication, in case of an anaphylactic reaction at home, the patient or caregiver should immediately contact an emergency care unit or emergency transportation as per standard medical practice, and contact study site personnel.

Appropriate drugs (eg, epinephrine, H1 and H2 antihistamines, and corticosteroids), and medical equipment to treat acute anaphylactic reactions must be immediately available. Study personnel must be trained to recognize and treat anaphylaxis (Lieberman et al 2010). Details on anaphylaxis management are provided in Appendix D.

Anaphylaxis will be defined as a serious reaction that is rapid in onset and may cause death (Simpson et al 2006). Anaphylaxis typically manifests as 1 of 3 clinical scenarios:

10. The acute onset of a reaction (minutes to hours) with involvement of the skin, mucosal tissue, or both, and at least 1 of the following: a) respiratory compromise or b) reduced blood pressure or symptoms of end-organ dysfunction
11. Two or more of the following that occur rapidly after exposure: involvement of the skin/mucosal tissue, respiratory compromise, reduced blood pressure or associated symptoms, and/or persistent gastrointestinal symptoms
12. Reduced blood pressure after exposure

In order to help understand the potential drug-relatedness of any acute reaction, a blood sample should be drawn during the event for additional ADA testing (if not already scheduled for this visit). Serum tryptase or other blood or urine testing relevant to the diagnosis of anaphylaxis may be obtained at a local lab at the discretion of the Investigator.

## **7. SAFETY REPORTING AND MEDICAL MANAGEMENT**

The Principal Investigator is responsible for ensuring that all staff involved in the study are familiar with the content of this section.

### **7.1 Definition of adverse events**

An adverse event (AE) is the development of an undesirable medical condition or the deterioration of a pre-existing medical condition following or during exposure to a pharmaceutical product, whether or not considered causally related to the product. An undesirable medical condition can be symptoms (eg, nausea, chest pain), signs (eg, tachycardia, enlarged liver) or the abnormal results of an investigation (eg, laboratory findings, ECG). In clinical studies, an AE can include an undesirable medical condition occurring at any time, including run-in or washout periods, even if no study treatment has been administered.

The term AE is used to include both serious and non-serious AEs.

### **7.2 Definitions of serious adverse event**

A serious adverse event (SAE) is an AE occurring during any study phase (ie, run-in, treatment, washout, follow-up), that fulfills 1 or more of the following criteria:

- Results in death
- Is immediately life-threatening
- Requires in-patient hospitalization or prolongation of existing hospitalization

- Results in persistent or significant disability/incapacity or substantial disruption of the ability to conduct normal life functions
- Is a congenital abnormality or birth defect
- Is an important medical event that may jeopardize the patient or may require medical intervention to prevent 1 of the outcomes listed above.

For further guidance on the definition of a SAE, see Appendix A to the Clinical Study Protocol

## **7.3 Recording of adverse events**

### **7.3.1 Time period for collection of adverse events**

Adverse events will be collected from the time the patient signs the informed consent, throughout the treatment period and including the follow-up period (through Week 28).

Serious adverse events will be recorded from the time of informed consent.

### **7.3.2 Follow-up of unresolved adverse events**

Any AEs that are unresolved at follow-up in the study are followed up by the Investigator for as long as medically indicated, but without further recording in the case report form (CRF). AstraZeneca retains the right to request additional information for any subject with ongoing AE(s)/SAE(s) at the end of the study, if judged necessary.

### **7.3.3 Variables**

The following variables will be collect for each AE;

- AE (verbatim)
- The date when the AE started and stopped
- Maximum intensity of the AE
- Whether the AE is serious or not
- Investigator causality rating against the Investigational Product (yes or no)
- Action taken with regard to investigational product
- AE caused subject's withdrawal from study (yes or no)
- Outcome.

In addition, the following variables will be collected for SAEs:

- Date AE met criteria for serious AE
- Date Investigator became aware of serious AE
- AE is serious due to
- Date of hospitalization
- Date of discharge
- Probable cause of death
- Date of death
- Autopsy performed
- Causality assessment in relation to Study procedure(s)
- Description of AE

It is important to distinguish between serious and severe AEs. Severity is a measure of intensity whereas seriousness is defined by the criteria in Section 7.2. An AE of severe intensity need not necessarily be considered serious. For example, nausea that persists for several hours may be considered severe nausea, but not a SAE unless it meets the criteria shown in Section 7.2. On the other hand, a stroke that results in only a limited degree of disability may be considered a mild stroke but would be a SAE when it satisfies the criteria shown in Section 7.2.

#### **7.3.4 Causality collection**

The Investigator will assess causal relationship between Investigational Product and each Adverse Event, and answer ‘yes’ or ‘no’ to the question ‘Do you consider that there is a reasonable possibility that the event may have been caused by the investigational product?’

For SAEs causal relationship will also be assessed for other medication and study procedures. Note that for SAEs that could be associated with any study procedure the causal relationship is implied as ‘yes’.

A guide to the interpretation of the causality question is found in Appendix A to the Clinical Study Protocol.

#### **7.3.5 Adverse events based on signs and symptoms**

All AEs spontaneously reported by the subject or reported in response to the open question from the study personnel: ‘Have you had any health problems since the previous visit/you were last asked?’, or revealed by observation will be collected and recorded in the CRF. When collecting AEs, the recording of diagnoses is preferred (when possible) to recording a list of signs and symptoms. However, if a diagnosis is known and there are other signs or

symptoms that are not generally part of the diagnosis, the diagnosis and each sign or symptom will be recorded separately.

### **7.3.6 Adverse events based on examinations and tests**

The results from protocol mandated laboratory tests and vital signs will be summarized in the clinical study report. Deterioration as compared to baseline in protocol-mandated laboratory values, vital signs should therefore only be reported as AEs if they fulfil any of the SAE criteria or are the reason for discontinuation of treatment with the investigational product.

If deterioration in a laboratory value/vital sign is associated with clinical signs and symptoms, the sign or symptom will be reported as an AE and the associated laboratory result/vital sign will be considered as additional information. Wherever possible the reporting Investigator uses the clinical, rather than the laboratory term (eg, anaemia versus low haemoglobin value). In the absence of clinical signs or symptoms, clinically relevant deteriorations in non-mandated parameters should be reported as AE(s).

Any new or aggravated clinically relevant abnormal medical finding at a physical examination as compared with the baseline assessment will be reported as an AE.

### **7.3.7 Disease progression**

When collecting AEs, the recording of diagnoses is preferred when possible to the recording of signs or symptoms. Asthma signs or symptoms such as wheeze, cough, chest tightness, breathlessness etc. will be recorded as AEs only when:

- The sign or symptom is serious according to definition, see Section 7.2
- The patient discontinues the study due to the sign or symptom.
- The sign or symptom is new to the patient or is not consistent with the patient's pre-existing asthma history as judged by the Investigator.

Asthma exacerbation should be recorded as an AE or SAE only if it fulfills any of the above criteria.

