### **3.6 Discontinuation of investigational product**

Patients will be discontinued from IP in the following situations:

1. Patient decision. The patient is free to discontinue treatment at any time without prejudice to further treatment.
2. Adverse event (AE) that, in the opinion of the Investigator, contraindicates further dosing
3. Risk to patient as judged by the Investigator or AstraZeneca
4. Severe non-compliance to study protocol
5. Eligibility requirement found not to be fulfilled (see Section 3.4)
6. Pregnancy
7. Lost to follow-up
8. Development of any study specific criteria for discontinuation:
  1. Anaphylactic reaction to the IP requiring administration of epinephrine
  2. Development of helminth parasitic infestations requiring hospitalization
  3. An asthma-related event requiring mechanical ventilation.
9. A patient who is self-administering IP who becomes unwilling or unable to continue to self-administer must be discontinued. Similarly, if a caregiver is giving the IP and becomes unwilling or unable to continue to administer IP to a patient, then that patient must be discontinued.

All patients who prematurely discontinue IP should return to the study center and complete the procedures described for the Premature IP Discontinuation (IPD) visit after 4 weeks ( $\pm 3$  days) and

---

 Patient is considered lost to follow up when any of the following attempts of contact are failed: -3 attempts of either phone calls, faxes or emails; - having sent 1 registered letter/certified mail; 1 unsuccessful effort to check the vital status of the patient using publicly available sources, if allowed by local regulations.

the procedures for the Follow-up visit after 12 weeks ( $\pm 3$ days) of the last IP administration. The reason(s) for premature discontinuation of IP should be recorded in the eCRF.

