##### **4.2.10.2 Adverse events**

Adverse events will be summarized for the on-study, on-treatment, and post-treatment periods, as defined in Section 3.3.1. All AEs will be listed regardless of treatment period.

An overall summary table will be produced showing the number and percentage of patients with at least 1 AE in any of the following categories: AEs, deaths due to AE, serious AEs (SAEs), and AEs causing discontinuation of IP (DAEs). The total number of AEs in the different AE categories in terms of AE counts will also be presented (ie, accounting for multiple occurrences of the same event in a patient).

Adverse events, DAEs and SAEs will be summarized by SOC and PT assigned to the event by MedDRA. For each PT, the number and percentage of patients reporting at least 1 occurrence will be presented, ie, for a patient multiple occurrences of an AE will only be counted once. Serious AEs causing discontinuation of the study treatment and SAEs causing discontinuation from the study will also be summarized.

Adverse events and SAEs (by PT) will be summarized by Investigator's causality and maximum intensity. If a patient reports multiple occurrences of the same AE within the same reported period, the maximum intensity will be taken as the highest recorded maximum intensity (the order being mild, moderate, and severe). Deaths will also be summarized in separate tables.

A summary of the most common (ie, frequency of >5%) AEs will also be presented.

Adverse events of injection site reactions (high level term of administration and injection site) will be summarized by PT for the on-treatment period. In addition, if there are sufficient amount of hypersensitivity events (standardized MedDRA query of hypersensitivity), it will also be summarized by PT for the on-treatment period as well as the on-study period.

Separate listings of patients with AEs, SAEs, death due to AE, or discontinuations due to AEs will be presented.

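### Protocol 7.3.7 does not make stopping IP a trigger for recording asthma worsening as an AE, so some IP stops may be absent from the SAP's DAE count

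*Protocol*

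**What the plan says.** Protocol 7.3.7 restricts when asthma signs and symptoms count as AEs. There are three alternative conditions, and any one is enough:

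- Seriousness, by the general SAE definition in Protocol 7.2.
- Leaving the study, worded as "The patient discontinues the study due to the sign or symptom".
- Novelty: the investigator judges that the patient has not had it before, or that it does not fit the asthma history.

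Exacerbations follow the same list: "Asthma exacerbation should be recorded as an AE or SAE only if it fulfills any of the above criteria".

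Protocol 3.6 treats the end of dosing as something other than the end of participation: "All patients who prematurely discontinue IP should return to the study center and complete the procedures described for the Premature IP Discontinuation (IPD) visit", with a Follow-up visit after that. The reason for stopping IP goes into the eCRF.

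For laboratory values and vital signs, Protocol 7.3.6 uses a different trigger. A deterioration is reported as an AE if it meets a seriousness criterion or if such changes "are the reason for discontinuation of treatment with the investigational product".

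SAP 4.2.10.2 includes "AEs causing discontinuation of IP (DAEs") as one of four categories in the overall AE table, and summarises DAEs again by system organ class and preferred term.

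**The concern.** The recording rule and the analysis category are keyed to different events. The rule asks whether the patient left the study, and the table asks whether the patient stopped IP. A DAE can be counted only if an AE record exists, so a case that the rule keeps out of the AE data cannot be recovered by the analysis.

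The population makes such a case plausible. Inclusion criterion 10 requires asthma that is not well controlled, so worsening during the study will often fit the patient's history and fail the new-or-atypical condition.

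Safety and tolerability is a stated objective, and there is no control arm against which under-recording would show. Any omission can act in one direction only: it lowers the DAE count.

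**Working it through.** The plan states no DAE rate, so there is no figure to reproduce. The check is a comparison of the rules, followed by one scaling calculation.

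**Step 1. Which IP stops meet no recording condition?** Take a patient whose asthma worsens and who stops IP. Protocol 7.3.7 then gives:

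| Serious? | New or atypical? | Leaves the study because of it? | AE under 7.3.7? |
|---|---|---|---|
| Yes | either | either | Yes |
| No | Yes | either | Yes |
| No | No | Yes | Yes |
| No | No | No | No |

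Only the last row falls through: non-serious, typical worsening in a patient who stops IP and stays for the remaining visits.

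**Step 2. Can a patient be in that row?** The grounds for stopping IP in Protocol 3.6 bear on this as follows.

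- The asthma-specific ground is an event needing mechanical ventilation. That would be expected to be serious, and so recorded.
- The ground of an AE that rules out further dosing presupposes that the investigator already regards the event as an AE.
- Patient decision, and risk as judged by the investigator or sponsor, need no AE. These are the main ways into the last row.

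**Step 3. Do the documents separate stopping IP from leaving the study?** In several places they do.

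- Protocol 3.6 schedules visits after IP has stopped.
- Protocol 7.3.3 collects the action taken on IP and withdrawal from the study as two AE variables.
- SAP 4.2.10.2 summarises SAEs that stop treatment apart from SAEs that end participation.
- Protocol 7.3.6 uses the IP trigger. Section 7.3.7 is the outlier.

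**Step 4. Would another planned output show the case?** SAP 4.2.1 tabulates reasons for not being treated and for withdrawing from the study, but names no table of reasons for stopping IP early. Exacerbations appear in SAP 4.2.2 only as history before entry. The reason for stopping IP is in the eCRF and would be listed, since SAP 4.1 lists all data, but neither document specifies a reconciliation of it with the AE data.

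**Step 5. Scale.** Inputs: about 120 treated patients (Protocol 8.2, SAP 1.3), and the full analysis set, meaning everyone who received IP, as denominator (SAP 2.1.2). If *k* patients are omitted:

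- understatement = 100 × *k* / 120 percentage points
- *k* = 1 gives 100 / 120 = 0.83 points
- *k* = 0 gives none

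The documents give no basis for choosing *k*.

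**The case against.** A reader might infer that asthma worsening is recorded only when the patient leaves the study, so that every worsening that stops only IP is lost. The documents do not support that. The three conditions are alternatives, and serious or atypical worsening is recorded whether or not the patient stays.

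The gap may be narrower still:

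- Whether worsening is atypical is left to the investigator, who may well judge an episode bad enough to end dosing as out of keeping with the patient's history.
- Protocol 5.2.1 and 7.3.6 require clinically significant new or aggravated physical findings to be reported as AEs, and SAP Section 6 relies on this. How that rule sits with the restrictive wording of 7.3.7 is arguable, but it may capture some cases.
- The documents use study and IP loosely. A patient or caregiver who cannot or will not inject at Week 8 is discontinued from the study in the protocol synopsis, Protocol 1.4 and SAP 1.2, but from IP in Protocol 4.2 and 6.6. Sites could read 7.3.7 as already covering IP stops. The eCRF instructions, which are not among these documents, may settle the matter.
- Keeping typical asthma out of the AE data is a deliberate choice, in a device study with no hypothesis tests.

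These points stand as limits on scope and certainty: the loss is possible, not demonstrated. They do not remove the mismatch. If sites read the bullet differently, the DAE count becomes harder to interpret, which is itself a reason to clarify it.

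**Conclusion.** The point holds in a limited form. Protocol 7.3.7 omits stopping IP as a recording trigger, while the SAP counts AEs that stop IP. Non-serious, typical worsening that ends dosing but not participation can therefore be absent from the DAE count. This rests on a literal reading of the second condition and on the patient remaining for the later visits.

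Each such patient would lower the DAE proportion by 0.83 points, assuming 120 in the full analysis set. A reader might go further and infer a definite understatement, or a tolerability profile that must look too favourable. The documents do not support either: they give no expected number of cases, and zero is compatible with everything in them.

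The primary device endpoints do not depend on AE recording. The correction is worth making because a stated rule causes the gap and closing it is cheap.

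**What to change.** 1. Reconcile Protocol 7.3.7 with 3.6, 7.3.6 and SAP 4.2.10.2 by rewording its second bullet so that it applies when the patient discontinues either IP or the study because of the sign or symptom. The exacerbation sentence refers back to the list and needs no separate change. Align the eCRF completion instructions if they repeat the old wording.
2. Before database lock, review the eCRF reasons for premature IP discontinuation for asthma worsening with no linked AE. Query each such case so that the investigator can enter the AE and it is counted as a DAE. If there are none, record that.

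The SAP edition is dated 25 September 2017 and the study was due to end by Q4 2017, so the second step is the more useful at this stage.

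Cost: a few words in the protocol, one data-management query, and a DAE count that may rise slightly. The change concerns what is recorded, not how patients are managed.
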